Recent studies have shown the efficacy of propolis on the reduction of fasting glucose and glycated hemoglobin,^{9,12,13} insulin resistance^{13,14} and postprandial glucose.¹⁴ However, there is a controversy between some results, as Fukuda et al. indicated that there was no significant difference in the parameters of glycemic control and insulin resistance.¹⁵ Likewise, Zakerkish et al. found no relevant reduction in fasting glucose after propolis supplementation.¹⁴

Therefore, there is a need for further studies, as there is no evidence from studies evaluating the effect of propolis on glycemic control in newly diagnosed patients without drug treatment. In addition to this, it has not been compared to the gold standard, metformin. Our hypothesis is that the administration of propolis or metformin modifies glycemic control in newly diagnosed patients without pharmacological treatment. The objective of this study is to evaluate the effect of propolis or metformin administration on glycemic control in recently diagnosed patients without pharmacological treatment.

MATERIAL AND METHODS

Selection criteria

Patients with a diagnosis of DM2 less than 5 years old and without pharmacological treatment for at least 3 months before entering the study, 30 to 60 years of age, mild to moderate physical activity, stable body weight for at least 3 months before the study, body mass index (BMI) of 25.0 to 34.9 kg/m², fasting serum glucose <13.88 mmol/L and postload serum glucose >11.10 mmol/L, will be criteria for entering the study. For the selection of individuals diabetes detection campaigns will be carried out in the metropolitan area of the City of Guadalajara. Women in the reproductive stage at risk of pregnancy, subjects who consumed drugs or supplements that modify the behavior of DM2, personal history of cardiovascular, kidney, pancreatic or thyroid disease and/or uncontrolled systemic arterial hypertension, known allergies to bee's sting or its derivative products, intolerance to metformin, total cholesterol (TC) \geq 6.20 mmol/L, triglycerides (TG) \geq 4.48 mmol/L will be excluded. Individuals with lack of tolerability to propolis, metformin and/or placebo, with adherence to treatment <80%, in the presence of a serious adverse event and/or who withdrew informed consent will be eliminated.

Study design

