A randomized, double-blind, placebo-controlled clinical trial of three pharmacological groups will be carried out, with the participation of 34 patients with a recent diagnosis of DM2 according to the criteria of the American Diabetes Association.¹⁶ The propolis capsules

will be obtained from NOW® of Chicago, Illinois (USA), containing 300 mg of propolis powder. Calcined magnesia will be used for the placebo. The allocation will be done by simple randomization using a list of numbers. All patients will receive for 12 weeks one capsule before the first bite of breakfast and another before the first bite of dinner. 12 of them took propolis (300 mg twice a day), another 12 received metformin (850 mg twice a day) and 12 more, placebo in the same pharmacological presentation. Each participant will receive medical nutritional therapy and will be instructed to continue with their normal physical activity.

Clinical and laboratory measurements

The medical history of each patient will be taken and anthropometric indices will be measured that included: height, weight, BMI, waist circumference (WC) and percentage of fat mass. In addition to blood pressure. Five visits will be completed during the study and a 2-h oral glucose tolerance test (OGTT) will be performed at the beginning and end of the intervention to calculate the areas under the curve (AUC) of glucose and insulin, total insulin secretion (insulinogenic index), first phase of insulin secretion (Stumvoll index) and insulin sensitivity (Matsuda index). For this, the individuals will take a solution with 75 g of anhydrous glucose dissolved in 300 ml of water in 5 minutes. After that, blood samples will be taken through a heparinized catheter before and at 30-min intervals (30, 60, 90 and 120 minutes) for 2 hours. At each visit, the presence of adverse events will be verified through the diary and compliance through the capsule count.

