To calculate low-density cholesterol, the Friedewald formula will be used: $LDL-c \text{ (mmol/L)} = TC \text{ (mmol/L)} - HDL-c \text{ (mmol/L)} - [TG \text{ (mmol/L)} / 2.2]$, while for very low density cholesterol (VLDL) the ratio of $TG \text{ (mmol/L)} / 2.2$ will be used. With a liquid chromatography the percentage of A1C will be calculated. The AUC of glucose and insulin will be calculated with the polygonal formula. Total insulin secretion will be assessed with the insulin index: $(\Delta AUC \text{ of insulin}) / (\Delta AUC \text{ of glucose})$. With the Matsuda $10000 / \sqrt{[(Glucose_0 \cdot Insulin_0) (Average \text{ of the PTOG} \cdot Average \text{ of the insulin in the PTOG})]}$ index the insulin sensitivity will be estimated, while with the index from Stumvoll $1283 + 1.829 \times \text{insulin}_{30'} - 138.7 \times \text{glucose}_{30'} + 3.772 \times \text{insulin}_0'$, the first phase of insulin secretion.

Sample size

For this study, the sample size it's calculated using a formula for mean difference¹⁷ with a statistical confidence of 95%, a statistical power of 80%, a standard deviation (SD) and an expected difference for fasting glucose, A1C and 2-h glucose of 0.6 mmol/L¹² and 1.0 mmol/L⁹, 0.5% and 0.8%¹², 2.3 mmol/L¹⁸ and 3.9 mmol/L¹⁹, respectively. While for metformin it's of 2.4 mmol/L²⁰ and 3.0 mmol/L²¹, 1.0% and 1.5%²², 3.5 mmol/L²³ and 5.5 mmol/L²⁴, respectively. A total of 12 patients is obtained for each group, including 20% of the expected loss.

Security measures

All patients will be informed about the possible adverse effects of propolis and metformin; they will have the emergency telephone numbers of the responsible and associated investigators.

STATISTIC ANALYSIS

The study will be designed to demonstrate the effect of propolis and metformin relative to placebo in terms of the outcome variables of effectiveness. Assuming there are no differences in propolis and metformin versus placebo regarding effectiveness in reducing glycemic control, it's calculated that approximately 36 randomized patients will provide ~80% power to demonstrate superiority.

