All statistical analyzes will be performed by intention to treat, which will be included randomized patients who receive at least 1 dose of study treatments and for whom there has a baseline value on measurements. First, with the Kruskal-Wallis test, it will be tested whether the baseline data group of primary and secondary variables come from the same population, that is, whether the 3 groups are comparable as no statistically significant differences are found.

Then, using the Kruskal-Wallis test, the final data will be evaluated and with those that will be significant a post-hoc test (Mann Whitney U) will be performed, comparing propolis versus metformin, propolis versus placebo, and metformin versus placebo. Differences between baseline and final measurements for primary and secondary variables will be calculated with the Wilcoxon test. Statistical comparisons will be made using a comparative type 1 error of 5% (two-tailed).

The safety profile analysis will include patients who receive at least 1 dose of study medication; safety data will be summarized using descriptive statistics.

FINANCING

The financing will be by own resources of the University of Guadalajara.

REFERENCES

1. IDF (International Diabetes Federation). International Diabetes Federation. Vol. 9, International Diabetes Federation. 2019. 144 p.
8. Khalil M. Biological activity of bee propolis in health and disease. *Asian Pac J Cancer Prev APJCP.* 2006;7:22–31.

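### Baseline-to-final Wilcoxon tests are planned at the same 5% level as the between-arm tests and are not labelled descriptive, so a change shared by all arms could be credited to propolis

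*Combined protocol and SAP*

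**What the plan says.** The combined protocol and SAP speaks to this in four places.

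- **STATISTIC ANALYSIS, tests.** Final values are compared across the three arms with Kruskal-Wallis, followed where significant by pairwise Mann-Whitney tests that include propolis against placebo. The next sentence reads "Differences between baseline and final measurements for primary and secondary variables will be calculated with the Wilcoxon test". One error rate then covers everything: "Statistical comparisons will be made using a comparative type 1 error of 5% (two-tailed". No order of importance is given, and nothing says that the baseline-to-final result is descriptive. The sentence does not say that the test is done within each arm, but that is its natural meaning, because it is listed apart from the between-group tests.
- **STATISTIC ANALYSIS, opening.** The aim is to show an effect of propolis and of metformin against placebo.
- **INTRODUCTION, hypothesis.** "Our hypothesis is that the administration of propolis or metformin modifies glycemic control in newly diagnosed patients without pharmacological treatment". No comparator is named.
- **Study design and Selection criteria.** "Each participant will receive medical nutritional therapy and will be instructed to continue with their normal physical activity". The start date of the nutritional therapy is not given and no run-in is described. Entry depends on glucose: "fasting serum glucose <13.88 mmol/L and postload serum glucose >11.10 mmol/L, will be criteria for entering the study". The 2-h glucose is also one of the three outcomes in the sample size section.

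**The concern.** A baseline-to-final change in the propolis arm adds together whatever the capsule does, whatever the nutritional therapy does, and any drift caused by selecting patients on a high value. The within-arm test cannot separate these. Only the contrast with placebo can, because the other parts are common to the arms.

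Taken literally, the hypothesis would be met by a significant Wilcoxon result in the propolis arm even if propolis were inert. A second trap is the pattern in which propolis changed significantly and placebo did not. It looks like a comparison but is not one, and it can arise by chance when both arms change equally. The plan tests change only within arms, since its between-arm tests use final values. At stake is the validity of the headline statement about propolis.

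**Working it through.** **Inputs from the documents.** Two-sided 5% (STATISTIC ANALYSIS). Twelve per group including 20% expected loss, so about 12/1.2 = 10 evaluable (Sample size). SD and expected difference for fasting glucose, A1C and 2-h glucose: propolis "0.6 mmol/L¹² and 1.0 mmol/L⁹, 0.5% and 0.8%¹², 2.3 mmol/L¹⁸ and 3.9 mmol/L¹⁹"; metformin "2.4 mmol/L²⁰ and 3.0 mmol/L²¹, 1.0% and 1.5%²², 3.5 mmol/L²³ and 5.5 mmol/L²⁴". I read the first number of each pair as the SD.

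**Assumed.** The size of the change shared by all arms, because the documents give no diet-only figure; normally distributed within-patient changes.

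**Step 1: the plan's own figure.** n per arm = 2 × [(1.960 + 0.842) × SD / difference]². The most demanding pair is metformin fasting glucose: 2 × 7.849 × (2.4/3.0)² = 10.05. Multiplied by 1.2 this is 12.06, which matches the stated 12. The other five pairs need 6 to 7 per arm before loss.

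**Step 2: within-arm test when propolis is inert.** Each patient's change is δ plus noise with standard deviation σ, with the same δ in propolis and placebo. Let p be the simulated probability that the exact two-sided Wilcoxon signed-rank test is significant at 5%. The arms are independent, so the chance that propolis is significant and placebo is not is p(1 − p).

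| Shared change δ/σ | p, n = 12 | p, n = 10 | p(1 − p), n = 12 |
|---|---|---|---|
| 0 | 4% | 5% | 4% |
| 0.3 | 14% | 13% | 0.14 × 0.86 = 12% |
| 0.5 | 32% | 29% | 0.32 × 0.68 = 22% |
| 0.8 | 67% | 60% | 0.67 × 0.33 = 22% |
| 1.0 | 85% | 78% | 0.85 × 0.15 = 13% |

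**Step 3: the same in the plan's units, n = 12.** The plan does not say whether its propolis SDs are of the value or of the change. Here they are taken as SDs of change.

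| Outcome (SD) | Shared fall assumed | Inert arm significant |
|---|---|---|
| Fasting glucose (0.6 mmol/L) | 0.25, 0.5, 0.75 mmol/L | 23%, 70%, 96% |
| A1C (0.5 points) | 0.2, 0.3, 0.5 points | 22%, 43%, 85% |
| 2-h glucose (2.3 mmol/L) | 1, 2, 3 mmol/L | 25%, 74%, 98% |

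With twice those SDs the middle cases drop to 23%, 14% and 25%.

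**Step 4: the comparison with placebo.** With the same shared change in both arms, the propolis-placebo Mann-Whitney test is significant in about 4% to 5% of trials whatever the size of δ, because δ cancels. With the Kruskal-Wallis test required first, the rate is 2.2% if all three arms are alike and 4.3% if metformin is 1.5 SD better.

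**Step 5: selection on 2-h glucose.** This applies only if the qualifying OGTT is also the baseline OGTT, which the plan does not state. With mean μ, standard deviation s and test-retest correlation ρ, the expected fall is (1 − ρ) × s × φ(a)/[1 − Φ(a)], where a = (11.10 − μ)/s. Assumed ranges: μ of 12 or 14; s of 2.3 or 3.5, from the sample size section; ρ of 0.6 or 0.8. The fall is then about 0.1 to 0.9 mmol/L, and selection alone gives 5% to 15% significant results. It is a minor contributor, and for this outcome only. The cap on fasting glucose in the same criterion pushes fasting values the other way, and A1C is not an entry criterion.

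**The case against.** The strongest reply is that the design already handles this. The trial is randomized, double-blind and placebo-controlled; the analysis section opens with an aim against placebo; the between-arm tests come before the Wilcoxon sentence; and that sentence attaches no claim of efficacy to its result. This stands as far as it goes. The protection is real, but it depends on those tests alone carrying the claim, and the section does not say that they do.

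Two further replies are correct and limit the point. The percentages in Steps 2 and 3 are detection rates for a real shared change. They become false positives only when the change is credited to propolis. They also follow from the assumed size of that change, so they show sensitivity and are not an expected error rate.

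Some stronger readings are tempting but are not supported:

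- A reader might infer that the nutritional therapy starts on the same day as the capsules. That is the natural reading of the Study design section, but no date is given.
- A reader might infer that between-arm power is weak, so that within-arm p-values will end up carrying the conclusion. The plan's own propolis figures say otherwise: standardized differences of 1.0/0.6 = 1.67, 0.8/0.5 = 1.60 and 3.9/2.3 = 1.70 give about 93% to 97% power with 12 per arm. Power would be low for smaller effects (about 20% at 0.5 SD and 42% at 0.8 SD), but doubting the planning inputs is a different point. How results will be reported cannot be known from the plan.
- A reader might infer that the sponsor intends to claim efficacy from within-arm tests. Nothing in the documents says so.

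**Conclusion.** The point holds as a gap in what the plan allows to count as evidence. Within-arm change cannot be attributed to the capsule, because all arms receive nutritional therapy and no run-in is described. Yet the plan tests that change at full significance level, with no descriptive label, beside a hypothesis without a comparator. If a shared change of 0.3 to 1.0 SD is assumed, an inert propolis arm of 12 is significant in about 14% to 85% of trials, and the misleading pattern of propolis significant and placebo not occurs in about 12% to 22%. The comparison with placebo stays at about 4% to 5%. The direction of the finding does not depend on the assumed size; the percentages do. The between-arm analysis itself is not made invalid by any of this. A correction is worthwhile because it closes an invalid route to the main conclusion by wording alone.

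**What to change.** 1. In STATISTIC ANALYSIS, state that any claim of effect for propolis or metformin rests only on the between-arm comparison with placebo.
2. Report within-arm change descriptively: median change with an interval, the three arms side by side. If the Wilcoxon tests are kept, label them clearly as secondary results that are not evidence of effect. Add that within-arm change cannot be attributed to the capsule, because all arms receive nutritional therapy.
3. In the Introduction, add to the hypothesis that the change in glycemic control is *compared with placebo, on top of medical nutritional therapy*. This brings it into line with the aim already stated in the analysis section.

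Stating when nutritional therapy begins relative to the baseline measurements would also help the reader, but it does not replace items 1 to 3.

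Cost: wording only, with no added patients, visits or assays. The downside is that within-arm p-values can no longer be used as evidence of effect.

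### The plan names no primary glycaemic outcome and no success rule across the three outcomes it sizes, although each is tested separately at 5%

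*Combined protocol and SAP*

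**What the plan says.** The Introduction gives a broad aim: "The objective of this study is to evaluate the effect of propolis or metformin administration on glycemic control". It also gives as a reason for the trial that for propolis "it has not been compared to the gold standard, metformin".

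The Sample size section lists three glycaemic outcomes in parallel, first for propolis ("a standard deviation (SD) and an expected difference for fasting glucose, A1C and 2-h glucose of 0.6 mmol/L", and so on) and then again for the active comparator ("While for metformin it's of 2.4 mmol/L", and so on). None is singled out.

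The Statistic analysis section says that both drugs are to be compared with placebo "in terms of the outcome variables of effectiveness", and that "approximately 36 randomized patients will provide ~80% power to demonstrate superiority". For each outcome the final data go through a Kruskal-Wallis test. Where that is significant, the three pairs of arms are compared by Mann-Whitney U. Before-after changes are tested too: "Differences between baseline and final measurements for primary and secondary variables will be calculated with the Wilcoxon test". The error rate is set per comparison: "Statistical comparisons will be made using a comparative type 1 error of 5% (two-tailed".

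So the plan presupposes a split into primary and secondary outcomes, but no section says which outcomes fall on which side. These sections read continuously, and nothing suggests that a list was blacked out.

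**The concern.** A superiority aim needs a statement of what counts as superiority. Here a significant propolis-placebo result on fasting glucose, A1C or 2-h glucose could be presented as an effect on glycaemic control, and the plan does not say whether one outcome, a named one, or all three must be significant.

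The Kruskal-Wallis test does not close the gap. It protects the pairwise tests within one outcome and does nothing across outcomes. It is also a test of all three arms together. If metformin works, the metformin arm makes it significant, and an inert propolis is then compared with placebo at close to 5% on each of the three outcomes. What is at stake is whether a favourable outcome could be picked after the data are seen.

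**Working it through.** **1. The plan's own sample size.** With two-sided 5% and 80% power, n per arm = 2 × [SD × (1.960 + 0.842) / difference]². The most demanding of the six SD/difference pairs is metformin on fasting glucose: 2 × (2.4 × 2.802 / 3.0)² = 10.05. Adding 20% for loss gives 10.05 × 1.2 = 12.06, the plan's 12 per group. The other five pairs need 6 or 7 per arm before loss. The calculation treats the three outcomes as parallel and makes no allowance for testing three.

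**2. Inputs for the illustration.**
- From the plan: the Kruskal-Wallis test at 5%, then Mann-Whitney at two-sided 5%; 12 per arm, or about 10 after loss; metformin effects in SD units of 3.0/2.4 = 1.25 (fasting glucose), 1.5/1.0 = 1.50 (A1C) and 5.5/3.5 = 1.57 (2-h glucose).
- Assumed, because the plan is silent: success means at least one significant propolis-placebo result among these three; correlation between outcomes of 0 to 0.9; normal data; exact Mann-Whitney test; the stated SDs apply to the final values that are tested.
- Propolis is set equal to placebo. Each setting has 40,000 simulated trials (simulation error about 0.2 percentage points).

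**3. How often the Kruskal-Wallis test lets the pairwise tests through.** For fasting glucose, A1C and 2-h glucose in turn: 84, 95 and 96% of trials at 12 per arm; 75, 89 and 92% at 10 per arm.

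**4. At least one false propolis-placebo result among three.**

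| Correlation | 12 per arm, two-sided | 12 per arm, favouring propolis | 10 per arm, two-sided | 10 per arm, favouring propolis |
|---|---|---|---|---|
| 0 | 12.7% | 6.5% | 12.0% | 6.0% |
| 0.3 | 12.3% | 6.3% | 11.8% | 5.8% |
| 0.5 | 11.6% | 5.8% | 11.1% | 5.6% |
| 0.7 | 10.3% | 5.2% | 10.0% | 4.9% |
| 0.9 | 8.1% | 4.0% | 7.7% | 3.9% |

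Check by hand: the rate for one outcome is about 4.4%, because the exact test is discrete at this size. Three independent outcomes give 1 − (1 − 0.044)³ = 12.6%. At a full 5% each, the figure would be 1 − 0.95³ = 14.3%.

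**5. How far the assumptions matter.**
- Propolis SDs in place of metformin SDs: 12.8 to 8.1% at 12 per arm and 12.3 to 8.0% at 10, so the choice of SD hardly moves the error rate.
- Uncorrected normal approximation to Mann-Whitney at 12 per arm: 9.1 to 14.5% two-sided, 4.5 to 7.5% favouring propolis.
- Neither drug works: 3.9 to 6.8% two-sided, 1.9 to 3.5% favouring propolis.
- One outcome named in advance: 3.9 to 4.6%.
- All three required: 0 to 1.7% if propolis is inert on all three. If it truly affects two, a false claim on the third completes the set in about 3.7% of trials. Neither exceeds the single-outcome rate.

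**The case against.** The strongest reply is that the 8-13% belongs to a rule the plan never states. It needs an any-one-of-three criterion, an inert propolis and a metformin effect of the planned size, all together. That stands. A reader might infer that this is the trial's false-positive rate, or that the sponsor means to claim success on any one outcome. The documents support neither; they are silent on the rule.

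The family of three is also an inference. These outcomes are used for sizing and are never called primary, and the plan also measures insulin indices, areas under the curve and lipids. The figure is therefore not an upper bound either, since a wider family could give more. The Mann-Whitney version is likewise left open.

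A reader might also infer that the three unadjusted pairwise tests within one outcome inflate the error. With three arms behind the Kruskal-Wallis test they do not: if the arms are not all equal, at most one pair can be, and the simulated single-outcome rate stays below 5%.

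Finally, per-comparison control can be a deliberate choice in a small trial. That is fair for exploratory work, but it sits poorly with a stated aim of superiority at about 80% power, and it does not supply the missing primary outcome.

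**Conclusion.** The gap is in the text and needs no simulation: no primary outcome is named, and no rule links three separately tested outcomes to a claim about propolis. Its size depends on the rule. Under an any-of-three reading, with metformin working and propolis inert, the false-result rate is about 8-13% (about 4-6.5% favouring propolis, against a nominal 2.5%), on the exact test and assumed correlations of 0.9 to 0. It is near 4-7% if neither drug works, and no higher than the single-outcome rate of about 4-5% if all three must be significant. The inflation is moderate and conditional, and it does not make the trial invalid. The plan should be changed because the change is cheap and removes the choice of outcome after the data are seen.

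**What to change.** In the Statistic analysis section, before unblinding:
- Name one primary glycaemic outcome (the sponsor's choice) for propolis versus placebo, tested at two-sided 5% behind its Kruskal-Wallis test.
- Test the other two in a pre-stated fixed sequence, each only if the one before is significant.
- Treat all other outcomes, propolis versus metformin, and the Wilcoxon before-after tests as secondary or descriptive. State whether metformin versus placebo is a separate claim.
- If success is meant to require all three outcomes, say so; no adjustment is then needed.

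With metformin working and propolis inert, the fixed sequence brings the two-sided error across the three outcomes to 4.2-4.5%.

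**Cost.** No extra patients or measurements. The primary outcome keeps its full power; later ones lose some. How much depends on which SDs in the Sample size section apply. Take 10 per arm, correlation 0.5, all three outcomes responding to propolis, and the example order A1C, 2-h glucose, fasting glucose. With the metformin SDs, power goes from 34, 59 and 12% to 34, 27 and 7%. With the propolis SDs, it goes from 90, 92 and 92% to 90, 84 and 80%.

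Holm across the three is an alternative (error 2.8-4.3%), but it costs every outcome something: with the metformin SDs, the chance of any propolis win falls from 67% to 49%. The sponsor would have to weigh that. Reconciling the two sets of SDs is a separate point and need not come first.
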